8.5.2 Echocardiography

For the assessment of the impact of QCC374 on right and left heart structure and function, echocardiography will be performed based on the clinical practice and local regulation. The duration between an acceptable baseline scan and initiation of dosing will be less than 21 days. In all patients, the baseline and follow-up imaging will be performed where possible using the same ultrasound scanner. The methods for assessment and recording are specified in the imaging manual/charter.

The coded medical images will be used primarily for analysis as described in this protocol; however, the images may also be used for the development and evaluation of new analysis methods directly related to the area of research that this study covers.

8.5.3 6-Minute Walk Test

A standardized 6MWT will be performed in accordance with ATS guidelines (ATS 2002). The 6MWT measures how many meters a person can walk in 6 minutes. Repeated measurement of the 6MWT over time has been used in studying numerous musculoskeletal, pulmonary, and cardiovascular conditions and is a validated outcome in investigational drug trials.

For the Borg score component, the patient will answer questions on a scale of one to ten in order to determine the patient's shortness of breath during the 6MWT. During the 6MWT the patient will be connected to a portable pulse oximeter via a finger probe and oximetry results will be monitored. As soon as the test is complete, the patient will be asked to sit down and the SaO₂, HR and Borg score values will be recorded.

Patients resting values of oxygen saturation (%), heart rate (b/min), blood pressure and Borg score will be recorded in the CRF before the test, at the end of the test and two minutes after the end of the test. Total distance walked (meters), the number and duration of any stops and whether the patient completed the test will also be recorded in the CRF.

Requirement of rescue medication including oxygen therapy and any adverse events occurring during the 6MWT will be recorded. If the patient is on chronic oxygen therapy, oxygen should be given at the standard rate (and at the same rate during each 6MWT procedure) or as directed by the investigator.

During screening at least two 6MWT must be performed at least 2 hours apart. The two values must be within 15% of one another. Additional 6MWT may be performed until two consecutive 6MWDs are within 15% of one another (maximum of 4 tests performed).

The site should record the values of both qualifying 6MWT in the CRF. The average of the two consecutive qualifying tests will be used as the baseline.

After screening, single 6MWTs will be performed according the Assessment schedule (Section 8.1). Every attempt should be made to conduct the 6MWT at about the same time of day.

Additional information on this assessment can be found in the SOM.

8.6 Safety

Safety assessments are specified below; methods for assessment and recording are specified in the SOM, with the Assessment Schedule ([Section 8.1](#)) detailing when each assessment is to be performed.

8.6.1 Spirometry

Spirometry testing will be performed according to the American Thoracic Society guidelines ([Miller et al 2005](#)) at screening to assess patients' eligibility for the study and as detailed in the Assessment schedule ([Section 8.1](#)).

The spirometry equipment will be supplied for the study. The same spirometry equipment should be used for all assessments performed by a subject. A limited number of staff, as designated by the investigator, will evaluate all patients at all visits throughout the entire trial. Where possible the same technician should perform all maneuvers for an individual subject. All staff conducting the spirometry tests must have received appropriate training which must be documented. Information on the procedures can be found in the SOM.

8.6.2 Chest X-ray

Standard CXR will be performed except for those who have had a valid X-ray done within 6 months of the screening visit to confirm eligibility. During the trial, there may be standard CXRs completed at the time of the RHC (if part of site's standard of care follow-up).

8.6.3 Physical examination

Information can be found in the SOM.

8.6.4 Vital signs

At multiple time points referenced in the Assessment Schedule ([Section 8.1](#)), Blood Pressure, Pulse and Body Temperature will need to be recorded.

8.6.5 Pulse oximetry

Oxygen saturations (%) will be measured by pulse oximetry using a SpO2 finger sensor. The timing of the assessments can be found in the Assessment Schedule ([Section 8.1](#)) and results will be recorded in the CRFs.

8.6.6 Height and weight

Height and weight will need to be recorded as referenced in the Assessment Schedule ([Section 8.1](#)).

8.6.7 Laboratory evaluations

Clinically relevant deviations of laboratory test results occurring during or at completion of the study must be reported and discussed with Novartis personnel. The results should be evaluated for criteria defining an adverse event and reported as such if the criteria are met. Repeated evaluations are mandatory until normalization of the result(s) or until the change is no longer clinically relevant. In case of doubt, Novartis personnel should again be contacted.

Hematology

Hemoglobin, hematocrit, red blood cell count, white blood cell count with differential and platelet count will be measured. In addition, aPTT and PT and INR will be assessed.

Clinical chemistry

Sodium, potassium, creatinine, urea, uric acid, chloride, albumin, calcium, alkaline phosphatase, total bilirubin, LDH, GGT, AST, ALT, CK, glucose, total cholesterol, triglycerides. If the total bilirubin concentration is increased above 1.5 times the upper limit of normal, direct and indirect reacting bilirubin should be differentiated.

Urinalysis

Urine test by dipstick e.g. Combur9: leucocytes, nitrite, pH, protein, glucose, ketones, urobilinogen, bilirubin, hemoglobin

If the dipstick result is positive for protein, nitrite, leucocytes and/or blood, the sample will be sent for microscopic analysis of white blood cells, red blood cells and casts.

8.6.8 Pregnancy and assessments of fertility

All pre-menopausal women who are not surgically sterile will have pregnancy testing. See the Assessment schedule ([Section 8.1](#)), for timing of the protocol required pregnancy testing; additional pregnancy testing may be performed to meet local requirements. A positive urine pregnancy test must be immediately confirmed with a serum β -hCG, and if the serum β -hCG is found to be positive, study treatment must be discontinued.

Refer to [Section 9.6](#) for details on Reporting Pregnancy.

8.6.9 Lung Volumes and DLCO

Lung volumes and DLCO measurements will be determined according to ATS guidelines ([Wanger et al 2005](#), [MacIntyre et al 2005](#)). Detailed procedures for lung volume and DLCO acquisition are provided in the SOM.

8.6.10 ECG

ECGs will be assessed locally. Full details of all procedures relating to the ECG collection and reporting are contained in the SOM.

8.7 Pharmacokinetics

All subjects who receive QCC374 (or matching placebo) will have blood samples collected as outlined in [Table 8-2](#) and [Table 8-4](#) ([Section 8.1](#)). Blood sampling times need to be adhered to sampling schedules.

In order to better define the PK profile, the timing of the PK sample collection may be altered based on emergent data. The number of samples/blood draws and total blood volume collected will not exceed those stated in the protocol.

8.7.1 PK Sample Collection

All samples will be given a unique sample number and a collection number (as listed in [Table 8-2](#) and [Table 8-4, Section 8.1](#)). Each site is to ensure the correct sample number is reflected on the respective tube. The actual sample collection time will be entered on the PK blood collection page of the CRF. Any problems with sampling will be documented within the CRFs.

Further details on sample collection, numbering, processing and shipment can be found in the SOM.

8.7.2 Bioanalytical Method

QCC374 and QCM441 concentrations in plasma samples will be determined by a validated LC-MS/MS method; the Lower Limit of Quantification (LLOQ) is 5 pg/mL for QCC374 and 20 pg/mL for QCM441. Biofluid concentrations will be expressed in mass per volume units and referring to the free base. Missing data will be labelled as such in the concentration data listings. Concentrations below LLOQ will be treated as zero in summary statistics for concentration data as well as for calculation of PK parameters.

Untreated samples (placebo) will not be analyzed.

PK samples remaining after completion of the determination of QCC374 and QCM441 may be used for exploratory assessment of metabolites or other bioanalytical purposes (e.g. cross check between different sites, stability assessment). Given the exploratory nature of the work, the analytical method used for those assessments will not be validated and results will not be reported in the clinical study report (CSR).

8.7.3 Calculation of PK Parameters

For standard pharmacokinetic abbreviations and definitions see the list provided at the beginning of this protocol.

The following pharmacokinetic parameters of QCC374 and QCM441 (where possible/applicable) will be determined using the actual recorded sampling times and non-compartmental method(s) with Phoenix WinNonlin (Version 6.2 or higher):

Primary: C_{max}, T_{max}, AUC_{last}, AUC_{tau} for Day 1 and Day 112

Secondary: T_{last}, T_{1/2}, T_{min}, C_{min}, fluctuation index, C_{av}, V_z/F (QCC374 only) and CL/F (QCC374 only) for Day 1 and Day 112.

Additional parameters may be determined if appropriate. To denote parameters determined at steady state "ss" will be used. The parameters AUC_{last}, AUC_{tau}, and C_{max} will be transferred into molar units using the molecular weight of QCC374 (443.58 g/mol) and QCM441 (415.23 g/mol) to enable the exposure comparison between the two analytes.

The linear trapezoidal rule will be used for AUC calculation. Regression analysis of the terminal plasma elimination phase for the determination of T_{1/2} will include at least 3 data points after C_{max}. If the adjusted R² value of the regression analysis of the terminal phase will be less than 0.75 and the extrapolated AUC will be greater than 20%, no values will be reported for AUC_{tau}, T_{1/2}, CL/F, and V_z/F.

Corporate Confidential Information

9 Safety monitoring

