HV	healthy volunteer
Hx/Su	Hypoxia/Sugen
i.t.	intra-tracheal
i.v.	Intravenous
ICH	International Conference on Harmonization of Technical Requirements for Registration of Pharmaceuticals for Human Use
IEC	Independent Ethics Committee
IPR	prostacyclin receptor
IRB	Institutional Review Board
IRT	Interactive Response Technology
LDH	lactate dehydrogenase
LLOQ	lower limit of quantification
LV	left ventricular
MAD	multiple ascending dose
MCT	Monocrotaline
mg	milligram(s)
ml	milliliter(s)
mPAP	mean pulmonary artery pressure
MTD	maximum tolerated dose
NOAEL	no observed adverse effect level
NT-proBNP	N-terminal prohormone of brain natriuretic peptide
NYHA	New York Heart Association
PA	pulmonary artery
PAH	pulmonary arterial hypertension
PCWP	Pulmonary Capillary Wedge Pressure
PD	pharmacodynamic(s)
PG	Pharmacogenetics
PH	pulmonary hypertension
PK	pharmacokinetic(s)

PVR	pulmonary vascular resistance
RA	right atrium
REB	Research Ethics Board
RHC	right heart catheterization
RV	right ventricular
SAD	single ascending dose
SAE	serious adverse event
SAP	Statistical Analysis Plan
SD	standard deviation
SOM	Site Operations Manual
SVR	systemic vascular resistance
TBL	total bilirubin
ULN	upper limit of normal
WHO	World Health Organization

Pharmacokinetic definitions and symbols

AUC _{0-t}	The area under the plasma (or serum or blood) concentration-time curve from time zero to time 't' where t is a defined time point after administration [mass x time / volume]
AUC _{last}	The area under the plasma (or serum or blood) concentration-time curve from time zero to the time of the last quantifiable concentration [mass x time / volume]
AUC _{tau}	The area under the plasma (or serum or blood) concentration-time curve from time zero to the end of the dosing interval tau [mass x time / volume]
AUC _{tau,ss}	The area under the plasma (or serum or blood) concentration-time curve from time zero to the end of the dosing interval tau at steady state [mass x time / volume]
C _{av,ss}	The average steady state plasma (or serum or blood) concentration during multiple dosing
CL	The systemic (or total body) clearance from plasma (or serum or blood) following intravenous administration [volume / time]
CL/F	The apparent systemic (or total body) clearance from plasma (or serum or blood) following extravascular administration [volume / time]
CL _r	The renal clearance from plasma (or serum or blood) [volume / time]

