- Patients who complete Visit 108 (Day 111) and do not wish to enroll in the extension study will receive study drug on the morning of Visit 109 (Day 112) and complete PK and indicated safety assessments. These patients will not receive the pm dose of study drug. The last visit for these patients is the End of Study Visit (Visit 202), 28 days after receiving last dose of study drug.

3.1.1 Part 1

[figure not shown]
Part 1 (Figure 3-2) will consist of 8 subjects, randomized in a 6:2 ratio to QCC374 or placebo. The planned bid dose levels in Part 1 are 0.03 mg, 0.06 mg and 0.12 mg. Subjects will begin dosing at 0.03 mg bid.

- On Day 4 the investigator will assess an individual subject's clinical status and reported adverse events and confirm that an individual subject can be up-titrated to 0.06 mg bid. This decision, made individually for every subject, will be based on the investigator's assessment of the severity of any adverse events, including adverse events typical of prostacyclins (e.g. headache, jaw pain, myalgia, flushing and nausea).
- On Day 7 the investigator will assess an individual subject's clinical status and reported adverse events and confirm that an individual subject can be up-titrated to the next planned dose level. This decision, made individually for every subject, will be based on the investigator's assessment of the severity of any adverse events, including adverse events typical of prostacyclins.
- On Day 14 the investigator will assess the patient's clinical status and reported adverse events. If the patient is not already receiving the maximum dose of 0.12 mg bid, the investigator will determine whether an individual subject can be up-titrated one dose level.

This decision, made individually for every subject, will be based on the investigator's assessment of the severity of any adverse events, including adverse events typical of prostacyclins.

- Following the Day 14 visit no further up-titrations are allowed. Subjects are allowed to continue in the trial even if their final dose after titration on Day 14 is not 0.12 mg.
- On Day 21, if the subject's dose was up-titrated on Day 14, a follow-up phone call visit will occur to review safety and tolerability.

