Serious adverse events	As Required																
Comments	As Required																

¹ Visit structure given for internal programming purpose only

² Domiciled in Clinic (optional)

³ If the subject was up-titrated at the Day 14 visit, a phone call for follow-up on subject safety and tolerability should be conducted 7 days later.

⁴ If a patient needs to stop study medication prematurely (for example, due to worsening of underlying PAH), then an attempt should be made to complete the Day 113 assessments, including a Blood Chemistry, Blood Hematology and Echocardiogram (unless these assessments were completed on Day 111). The investigator is responsible for making determination of what is safe and feasible. At a minimum, a safety evaluation must be completed.

⁵ Visit 109 (Day 112) must occur 1 day after Visit 108 (Day 111)

⁶ This visit is only for subjects who have completed the study treatment (Day 112) and do not wish to participate in Extension Study, or for subjects who discontinue study treatment early.

⁷ This 28 days post last treatment follow up visit is for those subjects who have either prematurely stopped study treatment, or those subjects who completed the study treatment, but do not wish to participate in the extension study.

⁸ The results of this assessment will only be recorded in the source data

⁹ Serum Pregnancy Test

¹⁰ Urine Pregnancy Test

¹¹ Within 2 hours after dose.

¹² During screening at least two 6MWT must be performed at least 2 hours apart. The two values must be within 15% of one another. Additional 6MWT may be performed until two consecutive 6MWDs are within 15% of one another (maximum of 4 tests performed).

¹³ Chest X-ray needs to be completed prior to randomization, but Chest X-ray post RHC can be used (if part of standard of care follow-up)

¹⁴ This to be completed post RHC

¹⁵ Echocardiogram can be completed any time during Day -21 to Day -1

¹⁶ The baseline RHC can be completed any time from Day -28 to Day -1. If the subject has a historical RHC within one month of the screening visit, this result can be used

Corporate Confidential Information

For all follow-up visits, the PK sample collection will take place during the visit, but the subject must record time of morning dose.

Table 8-2 Part 1 PK blood collection

Epoch	Visit Name	Visit Numbers	Day	Time (post-dose)	PK blood collection
Treatment	Titration	101	1	0m	X
				5m	X
				15m	X
				30m	X
				1h	X
				2h	X
				4h	X
				8h	X

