	Stable Dose Follow Up	109	112 -2 +2	0m	X
				5m	X
				15m	X
				30m	X
				1h	X
				2h	X
				4h	X
				8h	X
			12h	X	

NOTE: Additional visit information can be found in [Table 8-1](#)

Epoch	Screening		Treatment ⁴											Post Treatment Follow Up			
Visit Name	Screening	Baseline	Titration						Stable Dose Follow Up					Termination Visit	EOS Visit (28 days post last treatment)		
Visit Numbers ¹	1	2 ²	101 ²						103	104 ³	105	106	107	108 ²	109 ^{2,5}	201 ⁶	202 ⁷
Study Day(s)	-28 to -2	-1	1						7 ±1	14 ±1	28 ±2	56 ±2	84 ±2	111 ±2	112 ±2	113	140
Time (post-dose)	-	-	0m	15m	30m	2h	4h	-	-	-	-	-	-	0m	-	-	
Lung Volumes/DLCO	X																
ECG evaluation	X	X		X		X	X	X	X	X	X	X	X	X	X		
6-Minute Walk Test Corporate Confidential Information		X ¹²								X	X	X	X				
		X								X	X	X	X				
	X	X								X	X	X	X				
		X											X				
Chest X-ray Corporate Confidential Information		X ¹³											X ¹⁴				
		X								X	X	X	X				
		X											X				
		X											X				
		X											X				
Echocardiogram Corporate Confidential Information		X ¹⁵											X				
			X														
Right heart catheterization		X ¹⁶											X				
Drug dispensation			X					X	X	X	X	X					
Study drug administration ²⁰ Corporate Confidential Information			Study Drug Administration will be bid - refer to Section 3.1 and Site Operations Manual														
			X ¹⁷														
PK blood collection ¹⁸	See Table 8-4 below																

Epoch	Screening		Treatment ⁴											Post Treatment Follow Up		
Visit Name	Screening	Baseline	Titration					Stable Dose Follow Up					Termination Visit	EOS Visit (28 days post last treatment)		
Visit Numbers ¹	1	2 ²	101 ²					103	104 ³	105	106	107	108 ²	109 ^{2,5}	201 ⁶	202 ⁷
Study Day(s)	-28 to -2	-1	1					7 ±1	14 ±1	28 ±2	56 ±2	84 ±2	111 ±2	112 ±2	113	140
Time (post-dose)	-	-	0m	15m	30m	2h	4h	-	-	-	-	-	-	0m	-	-
Study/Epoch completion information		X												X		X
Concomitant medications	As required															
Adverse events	As required															
Serious adverse events	As required															
Comments	As required															

¹ Visit structure given for internal programming purpose only

² Domiciled in Clinic (optional)

³ If the subject was up-titrated at the Day 14 visit, a phone call for follow-up on subject safety and tolerability should be conducted 7 days later.

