⁴ If a patient needs to stop study medication prematurely (for example, due to worsening of underlying PAH), then an attempt should be made to complete the Day 113 assessments, including a Blood Chemistry, Blood Hematology and Echocardiogram (unless these assessments were completed on Day 111). The investigator is responsible for making determination of what is safe and feasible. At a minimum, a safety evaluation must be completed.

⁵ Visit 109 (Day 112) must occur 1 day after Visit 108 (Day 111)

⁶ This visit is only for subjects who discontinue study treatment early.

⁷ This 28 days post last treatment follow up visit is for those subjects who have either prematurely stopped study treatment, or those subjects who completed the study treatment, but do not wish to participate in the extension study.

⁸ The results of this assessment will only be recorded in the source data

⁹ Serum Pregnancy Test

¹⁰ Urine Pregnancy Test

¹¹ Within 2 hours after dose.

¹² During screening at least two 6MWT must be performed at least 2 hours apart. The two values must be within 15% of one another. Additional 6MWT may be performed until two consecutive 6MWDs are within 15% of one another (maximum of 4 tests performed).

¹³ Chest X-ray needs to be completed prior to randomization, but Chest X-ray post RHC can be used (if part of standard of care follow-up)

¹⁴ This to be completed post RHC

¹⁵ Echocardiogram can be completed any time during Day -21 to Day -1

¹⁶ The baseline RHC can be completed any time from Day -28 to Day -1. If the subject has a historical RHC within one month of the screening visit, this result can be used

Corporate Confidential Information

For all follow-up visits, the PK sample collection will take place during the visit, but the subject must record time of morning dose.

¹⁹ Blood pressure should be collected in the sitting position and then repeated after 3 minutes in the standing position.

²⁰ For patients who performed Visit 108 (Day 111) and do not wish to continue into the extension study, the last dose administration will be the morning dose on Visit 109, with no dose administration in the afternoon.

Table 8-4 Part 2 PK blood collection

Epoch	Visit Name	Visit Numbers	Day	Time (post-dose)	PK blood collection
Treatment	Titration	101	1	0m	X
				5m	X
				15m	X
				30m	X
				1h	X
				2h	X
				4h	X
				8h	X
	Stable Dose Follow Up	109	112 -2 +2	0m	X
				5m	X
				15m	X
				30m	X
				1h	X
				2h	X
				4h	X
				8h	X

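### Day 112 AUClast can run to 12 h in Part 1 but only to 8 h in Part 2, while PK parameters are summarised by dose level with no common window

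*Protocol*

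**What the plan says.** **Sampling.** "Table 8-2 Part 1 PK blood collection" lists Day 1 samples from pre-dose to 8 h and Day 112 samples from pre-dose to 12 h. "Table 8-4 Part 2 PK blood collection" ends at 8 h on both days. The assessment schedules agree: only the Part 1 schedule has a 12 h column at Visit 109.

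**Parameters.** The Protocol's PK definitions run AUClast from time zero "to the time of the last quantifiable concentration". Protocol 8.7.3 and SAP 5.1 make Cmax, Tmax, AUClast and AUCtau primary PK parameters on Days 1 and 112, with Tlast among the secondary ones. SAP 5.1 converts AUClast, AUCtau and Cmax to molar units so that the QCM441/QCC374 ratio can be formed. A fixed-window AUC0-t, "where t is a defined time point after administration", is in the definitions list but is not among the planned parameters.

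**Grouping.** Protocol 11.1 and SAP 4 pool the two parts. Protocol 11.5.2 lists PK parameters by dose level, study day and subject; SAP 5.2 summarises them by dose level. Neither names part.

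**Doses.** Part 1 (8 subjects, "randomized in a 6:2 ratio to QCC374 or placebo") has levels 0.03, 0.06 and 0.12 mg bid. Part 2 (about 30 subjects, 2:1) has 0.03 and 0.06 mg in Protocol 3.1.2. SAP 1.4 still describes titration to 0.12 mg in both parts; the two documents must be reconciled.

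**Reporting rule.** Under Protocol 8.7.3 the terminal regression "will include at least 3 data points after" Cmax. AUCtau, T1/2, CL/F and Vz/F are not reported if adjusted R2 is "less than 0.75 and the extrapolated AUC will be greater than 20" percent. The SAP does not repeat this rule.

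**The concern.** The end point of AUClast depends on when sampling stops. Two subjects with identical Day 112 exposure would get different AUClast values if one was in Part 1 and the other in Part 2, provided the 12 h concentration is quantifiable. In the current Protocol, 0.12 mg occurs only in Part 1, so that row is always on the longer sampling grid, while 0.03 and 0.06 mg can combine both grids in one row. A reader comparing dose levels would see part of the sampling schedule as exposure. The ratio is not protected by being a ratio: a metabolite that falls more slowly than its parent has more of its area between 8 and 12 h.

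AUCtau aims at the same 12 h interval for everyone, but from an 8 h profile it must be completed from 8 to 12 h. It is then subject to a reporting rule whose key term, the extrapolated AUC, has no stated end point.

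**Working it through.** There is no planned figure to reproduce. The documents give the sampling times and the LLOQs (5 pg/mL for QCC374, 20 pg/mL for QCM441; Protocol 8.7.2) but no half-life in the visible text. Half-lives below are assumptions.

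**1. Window ratio.** For mono-exponential decline with k = ln 2 / half-life, AUC0-12/AUC0-8 = (1 − e^(−12k)) / (1 − e^(−8k)). The last column applies the Protocol's linear trapezoid to 0, 5, 15 and 30 min and 1, 2, 4, 8 (and 12) h.

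| Half-life (h) | Formula | Trapezoid |
|---|---|---|
| 1 | 1.004 | 1.005 |
| 2 | 1.050 | 1.055 |
| 4 | 1.167 | 1.170 |
| 6 | 1.243 | 1.246 |
| 12 | 1.351 | 1.352 |

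This is the full gap between a 0.12 mg subject (Part 1) and a Part 2 subject, after allowing for dose. If the 12 h sample is below the LLOQ, AUClast stops at 8 h or earlier in both parts and the gap disappears.

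**2. Mixing within a level.** Part 2 has about 30 × 2/3 = 20 active subjects and Part 1 at most 6. If the window ratio is r, the geometric mean of a mixed row shifts by r^(share from Part 1).

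- Upper case, all 6 Part 1 subjects at 0.06 mg with all 20 from Part 2: r^(6/26) = 1.011, 1.036 and 1.072 at 2, 4 and 12 h.
- Two Part 1 subjects among 22: r^(2/22) = 1.004, 1.014 and 1.028.

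The upper case leaves nobody at 0.12 mg, so it cannot occur together with the full gap in step 1.

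**3. QCM441/QCC374 ratio.** Assume instantaneous parent input, first-order formation, steady state and tau = 12 h. Then M(t) is proportional to e^(−kp·t)/(1 − e^(−12kp)) − e^(−km·t)/(1 − e^(−12km)), up to sign. The shift is the metabolite's AUC0-12/AUC0-8 divided by the parent's.

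- Parent 2 h: 1.135 with a metabolite half-life of 2 h (taken as the limit), 1.250 with 4 h.
- Parent 1 h: 1.097 and 1.229.

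So the ratio can move even when the parent's own AUClast barely does.

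**4. Extrapolated AUC.** With the last sample at 8 h, the share extrapolated to infinity is e^(−8k). The share extrapolated to tau is (e^(−8k) − e^(−12k)) / (1 − e^(−12k)). At an assumed 4 h half-life these are 25.0% and 14.3%, on opposite sides of the 20% threshold. At 2 h they are 6.2% and 4.8%, both below it.

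**The case against.** The case against giving this weight is good, and most of it stands.

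- AUCtau is also a primary PK parameter, the ratio is planned for AUCtau and Cmax too, and Tlast and by-subject listings let a reader see the window behind each AUClast. This limits the harm. It does not remove it, because a Part 2 AUCtau on Day 112 needs completion beyond the last sample.
- That dose-level tables combine the parts is an inference from the general pooling sentence and from part not being named. No sentence says so outright.
- PK is descriptive, PK/PD analysis is marked not applicable (Protocol 11.5.3), and no dose-proportionality or accumulation test is visible. A Day 1 versus Day 112 comparison already spans doses in anyone up-titrated.
- The Protocol describes clearance as rapid or fast (1.1, 3.7, 3.7.2). That does not fix the plasma half-life after inhalation, but it is the only visible guide and points to the low end of the range.
- Because AUCtau is the only planned AUC that needs extrapolation and no AUC to infinity is defined, reading the rule to tau is natural. Day 1 CL/F leaves some doubt.

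A reader might also infer that the joint condition in 8.7.3 is a mistake, and that T1/2 and Vz/F should be withheld whenever adjusted R2 is below 0.75. It is true that poorly fitted slopes pass when extrapolation is 20% or less, but the remedy does not follow. In simulated 8 h profiles (mono-exponential, log-normal error, fit on 2, 4 and 8 h, rule read to tau), the stricter screen changes the share of reported T1/2 values wrong by more than 2-fold as follows:

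- true half-life 2 h, log-SD 0.4: from about 3% to 1.6%;
- 4 h, log-SD 0.4: from about 9.5% to 10.3%;
- 4 h, log-SD 0.6: from about 22% to 26%, with the median T1/2 moving from 0.80 to 0.68 of the true value.

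Whether it helps depends on a half-life and an error that the documents do not give.

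**Conclusion.** The mismatch is real but minor. Day 112 AUClast and the metabolite/parent ratio built on it have no common window across parts, and the planned grouping does not separate the parts. The size rests on assumed half-lives and a quantifiable 12 h sample: for AUClast 0 to 5% at 1 to 2 h, 17% at 4 h and 35% at 12 h between a Part 1 and a Part 2 subject, and no more than about 1 to 7% (2 to 12 h) in a mixed row. Under the model used, the ratio shifts by about 10 to 25%.

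The documents do not support reading the upper figures as likely, nor the view that the dose-level PK summaries are invalid. The undefined extrapolation term is a supporting clarification, not a second defect of equal weight. The PVR analysis is untouched.

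**What to change.** In Protocol 8.7.3 and SAP 5.1 to 5.2, with no new samples:

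1. Add AUC0-8h for QCC374 and QCM441 on Day 1 and Day 112. Use it, alongside AUCtau, for summaries across dose levels and parts and for the QCM441/QCC374 ratio.
2. Present AUClast by part, or with its Tlast.
3. State whether the extrapolated AUC in the reporting rule is to tau or to infinity, and carry the sentence into the SAP.
4. Keep the joint condition, and list adjusted R2 beside each reported T1/2 and Vz/F so that weak slopes are visible.

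The cost is a few sentences and one derived parameter per analyte and day. AUC0-t is already defined and 8.7.3 leaves room for further parameters. AUC0-8h ignores exposure after 8 h, which is why it should stand beside AUCtau and not replace it.
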